8.4.4 Safety Analysis

All data on any and all adverse events occurring during the baseline testing, 2 week period in which tDCS is being administered, and the 12 week interval between the end of tDCS and completion of the study will be used for an overall study safety analysis.

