3.1 General Design

This is a double-blind, sham-controlled, crossover study. Groups will be counterbalanced according to PPA subtype. All participants will undergo baseline language testing and neuroimaging prior to receiving 10 treatment sessions over 2 weeks (Monday-Friday) of either real or sham tDCS paired with mCILT. Immediate post-treatment, 6 week and 12 week follow-ups will be obtained. Participants will then crossover into the second portion of the study whereby they will receive the opposite treatment protocol (real or sham tDCS + mCILT) and an additional 24 week follow-up. Treatment must take place within 2 days to 4 weeks of baseline testing. The overall timeline for each subject's participation is indicated below in Figure 1.

Figure 1: Timeline for each subject

Enrollment	Baseline MRI	Baseline 1	Baseline 2	Treatment	Follow-up	Follow-up MRI	6 week Follow-up	12 week Follow-up	12 week Follow-up MRI	
SCREENING	VISIT 1**	VISIT 2*	VISIT 3*	Visit 4-13	VISIT 14*	VISIT 15**	VISIT 16*	VISIT 17*	VISIT 18**	
- Informed Consent - Screening Forms - Demographics Form	MRI	-CCRSA -WAB 1 -CILT 1 -NWRT -LTROG Oral -PPT Picture -NACC Word Reading -NACC Sentence Repetition	-WAB 2 -CILT 2 -PRT -DDK -LTROG Written -PPT Words -Story -NACC Sentence Reading	tDCS mCILT OR Sham tDCS mCILT	+	- WAB - CILT - NWRT - PRT - LTROG Oral & Written - PPT Picture & Words - NACC Word reading, Sentence Reading & Repetition - DDK - CCRSA - Story	MRI	- WAB - CILT - NWRT - PRT - LTROG Oral & Written - PPT Picture & Words - NACC Word reading, Sentence Reading & Repetition - DDK - CCRSA - Story	-CCRSA -WAB 1 -CILT 1 -NWRT -LTROG Oral -PPT Picture -NACC Word Reading -NACC Sentence Repetition	MRI
~ 1 hour	~ 1 hour	~ 3 hrs	~ 3 hrs	~ 1.5 hrs	~ 3 hrs	~ 1 hour	~ 3 hrs	~ 3 hrs	~ 1 hour	

CONFIDENTIAL

Crossover Baseline	Crossover Treatment	Crossover Follow-up	Crossover Follow-up MRI	Crossover 6 week Follow-up	Crossover 12 week Follow-up	Crossover 12 week Follow-up MRI	Crossover 24 week Follow-up
VISIT 19*	VISIT 20-29	VISIT 30*	VISIT 31**	VISIT 32*	VISIT 33*	VISIT 34**	Visit 35

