3.1.3 Study Intervention Phase

In the treatment phase, there will be 10 sessions of tDCS + mCILT over 2 consecutive weeks (Monday-Friday) in which 20 minutes of 1.5mA tDCS will be delivered to the left hemisphere. During each treatment session, a 60-90 minute session of mCILT will be simultaneously performed.

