3.1.5 Allocation to Interventional Group

Participants will be semi-randomized using a predetermined list generated by excel. Since this is a crossover study, all participants will eventually receive real stimulation - only the order will differ. Half of our participants will receive real tDCS first, and the other half will receive sham tDCS first. All participants will participate in mCILT.

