3.2.3 Primary Safety Endpoints [if applicable]

The risks from language tasks and MRI imaging are minor. Data on adverse events occurring during the 4 weeks in which tDCS is being administered will be collected by asking subjects at the beginning and end of every session if they have noted any adverse effects or new symptoms since their most recent. Reports of adverse effects from tDCS and other aspects of the study (brain imaging, language tasks and mCILT) will serve as the primary safety endpoint.

4 Study Population and Duration of Participation

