6.4.6 Visits 19-35 (Crossover)

Participants will crossover into the second half of the study after the 12 week follow-up. Visits 18 & 19 will serve as Baseline and then all study procedures will exactly match the first half of the study. The crossover will include an additional follow-up visit at 24 weeks.

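### Section 8.4.4 sets a safety analysis window for one tDCS course, but the trial has two courses and follows the second for 24 weeks

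*Combined protocol and SAP*

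**What the plan says.** Section 8.4.4 (Safety Analysis) lists the periods whose adverse events count: baseline testing, then the "2 week period in which tDCS is being administered, and the 12 week interval between the end of tDCS and completion of the study". Events from those periods "will be used for an overall study safety analysis". The section does not name a course and does not mention real or sham.

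Other sections describe a longer trial:

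- 3.1 (General Design): "Participants will then crossover into the second portion of the study whereby they will receive the opposite treatment protocol". Each course is ten weekday sessions over two weeks (3.1.3).
- 6.4.6 (Crossover): "Participants will crossover into the second half of the study after the 12 week follow-up", and "The crossover will include an additional follow-up visit at 24 weeks". Section 3.1.4 gives the same 24-week visit.
- 3.1.5 (Allocation): "Half of our participants will receive real tDCS first, and the other half will receive sham tDCS first".
- 3.2.3 (Primary Safety Endpoints): "Data on adverse events occurring during the 4 weeks in which tDCS is being administered will be collected".
- 9.2 has every adverse event in the study period recorded, and 8.5 makes the whole randomized crossover population the analysis population.

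**The concern.** Section 8.4.4 is the only place that says which adverse events are analysed. Its sequence of baseline, two weeks of stimulation and twelve weeks to the end fits a single-course trial. It disagrees with the rest of the protocol on how many weeks of stimulation there are and on when the study ends.

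Each participant receives real stimulation in only one of the two courses. An analysis that keeps one course therefore drops all real exposure for one sequence group. Adverse event reports are the trial's primary safety measure and 9.8.2 provides no DSMB, so the events to be analysed should not be left to interpretation.

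There is a second, smaller gap: no section plans a tabulation by condition. Section 12.1 warns that sham can produce side effects like those of real stimulation, because it includes about 30 seconds of real current. Counts by condition would therefore be informative, and the crossover design can supply them.

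**Working it through.** **Inputs.** Ten sessions per course at five per week (3.1.3); two courses (3.1, 6.4.6); last follow-up at 12 weeks after the first course and 24 weeks after the second (3.1.4, 6.4.6); 62 participants, half in each sequence (4.5, 3.1.5); attrition 15% historical and 25% planned (8.3).

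**1. The plan's own figures.** One course is 10 / 5 = 2 weeks, and one course plus follow-up is 2 + 12 = 14 weeks. This reproduces 8.4.4, but for one course only. Two courses give 2 x 2 = 4 weeks of stimulation, which reproduces 3.2.3.

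**2. Length of the design.** From first session to last visit the minimum is (2 + 12) + (2 + 24) = 40 weeks. This leaves out baseline testing and any gap before the crossover course; 4.4 gives about 12 months in all.

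**3. What each reading of 8.4.4 covers, of those 40 weeks.**

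| Reading | Weeks covered | Left out |
|---|---|---|
| A. First course only | 14 (14/40 = 35%) | the crossover course and its 24 weeks: 2 + 24 = 26 |
| B. Crossover course only | 14 (35%) | the first course and its 12 weeks, plus crossover weeks 12 to 24: 14 + 12 = 26 |
| C. Applied to each course | 2 x 14 = 28 (70%) | crossover weeks 12 to 24: 12 |

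Reading A fits the order of the list and the 12-week length. Reading B fits the statement that the window ends when the study does, although the crossover component ends at 24 weeks, not 12.

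**4. Real courses left out.** Each sequence group has 62 / 2 = 31 participants, so 31 real courses fall in each period. If all complete, A or B leaves out 31 / 62 = 50%. If attrition *a* all falls before crossover and is even across groups, the crossover period holds 31(1 - *a*) real courses:

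- 15%: 31 x 0.85 = 26.35, total 57.35. Reading A omits 26.35 / 57.35 = 46%; B omits 31 / 57.35 = 54%.
- 25%: 31 x 0.75 = 23.25, total 54.25. Reading A omits 23.25 / 54.25 = 43%; B omits 31 / 54.25 = 57%.

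Reading C leaves out no course.

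**5. Effect on what zero events can exclude (reading A).** The one-sided 95% upper bound with no event of a given type among *n* exposed is 1 - 0.05^(1/*n*). With *n* = 31 it is 9.2%. With both courses analysed it would be 4.7% at *n* = 62, or 5.4% at *n* = 54 (25% attrition). Under reading C this loss does not arise.

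**The case against.** The best reply is that 8.4.4 describes the window per course, as the protocol does elsewhere. The Study Summary gives stimulation as lasting two weeks, and 12.3 promises two weeks of CILT, although participants have two courses. Section 6.4.6 says the crossover procedures match the first half. The opening of 8.4.4 is sweeping, and 8.5 brings in the full crossover population. Section 7.7 expects adverse effects at the time of stimulation, so the weeks that a per-course reading omits are the ones least likely to matter.

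Much of this stands. The per-course reading is plausible and may be what was meant, so the loss of a whole course is conditional. It does not repair the text. Section 9.2 governs what is recorded and 8.5 governs who is analysed; neither sets the time window. The sweeping phrase is limited by the periods listed after it. A per-course window still stops 12 weeks short of the last visit.

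Four stronger inferences are tempting, and the documents do not support them:

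- *That the crossover course is the one dropped, with the sham-first group's real stimulation.* No course is named, and the reference to study completion could point to the second.
- *That half of the real exposure is bound to be lost.* This needs a single-course reading and full completion.
- *That the word overall means real and sham events will be pooled.* It may simply mean the whole study. The section is silent on a split and does not rule one out. The data for one exist: codes are logged each session (5.5), symptoms are documented each session (7.7), and the PI judges relatedness (9.3).
- *That events will go uncollected.* Sections 3.2.3 and 9.2 cover both courses.

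**Conclusion.** The window in 8.4.4 contradicts the two-course design, the 4 weeks in the safety endpoint and the 24-week crossover follow-up. No reading of it covers the whole trial.

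The size depends on the reading. As a single course, it omits one course and one sequence group's only real stimulation: 31 of 62 real courses with full completion. With attrition before crossover, the share is 43% to 46% if the first course is kept and 54% to 57% if the second is. As a per-course window, the omission is crossover weeks 12 to 24. These shares assume an even split of 62, and the attrition figures assume that every loss precedes crossover.

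This is a defect in the definition of the analysis, not in data collection, and it can be corrected in full before analysis. The lack of a planned tabulation by condition is an omission to fill, not a stated decision to pool.

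**What to change.** Replace the window in 8.4.4 with one running from consent through Visit 35, covering both courses and all follow-up, and reconcile it with 3.1.4, 3.2.3, 6.4.6 and 9.2.

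Add that adverse events will be tabulated by condition received (real or sham) in each treatment period, per participant and per session. Show baseline events and late follow-up events separately, and state in advance where a treatment period ends and late follow-up begins. Assigning every event to the most recent course would credit one occurring 24 weeks later to that condition, and nothing in the documents supports such a rule.

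The cost is one revised sentence and one more table. No new data are needed.

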9.2 Recording of Adverse Events

At each contact with the participant, the researchers will seek information on adverse events by specific questioning and, as appropriate, by examination. Information on all adverse events will be recorded immediately in the source document, and also in the appropriate adverse event module of the case report form (CRF). All clearly related signs, symptoms, and abnormal diagnostic procedures results will be recorded in the source document.

All adverse events occurring during the study period will be recorded. The clinical course of each event will be followed until resolution, stabilization, or until it has been determined that the study treatment or participation is not the cause. Serious adverse events that are still ongoing at the end of the study period will be followed up to determine the final outcome. Any serious adverse event that occurs after the study period and is considered to be possibly related to the study treatment or study participation will be recorded and reported immediately to the chair of the DSMB.

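### The safety analysis window in 8.4.4 describes a one-course trial and does not fit the two-course crossover: it holds one unnamed course or, read per course, stops 12 weeks before the final visit

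*Combined protocol and SAP*

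**What the plan says.** The combined protocol and SAP touches the adverse-event window in three places.

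- **Analysis (8.4.4).** The analysis uses all adverse events from baseline testing and the "2 week period in which tDCS is being administered, and the 12 week interval between the end of tDCS and completion of the study", for what it calls an overall safety analysis.
- **Primary safety endpoint (3.2.3).** "Data on adverse events occurring during the 4 weeks in which tDCS is being administered will be collected" by questioning at the start and end of every session. The next sentence defines the endpoint itself. It includes adverse effects of imaging, language tasks and mCILT as well as of tDCS, and it states no time limit.
- **Recording (9.2).** "All adverse events occurring during the study period will be recorded", with questions about events at each contact.

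The schedule is set elsewhere. Section 3.1 gives "10 treatment sessions over 2 weeks (Monday-Friday) of either real or sham tDCS paired with mCILT" as the first course, with follow-up to 12 weeks. After the crossover, "they will receive the opposite treatment protocol (real or sham tDCS + mCILT) and an additional 24 week follow-up". Section 6.4.6 repeats this: "The crossover will include an additional follow-up visit at 24 weeks". Section 7.5 counts the 6-, 12- and 24-week assessments from the completion of tDCS. Section 3.1.5 assigns half the participants to each order, and 4.5 plans up to 62 participants.

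**The concern.** Section 8.4.4 has two figures that can be checked against the schedule, and neither agrees. It has two weeks of tDCS where the design has four. It puts 12 weeks between the end of tDCS and the end of the study where the design has 24.

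The mismatch matters because 8.4.4 is the prespecified rule for which events are analysed. If it is applied to one course only, half of the planned real exposure and half of the sham exposure drop out. Each participant's own comparison of real with sham goes too. If it is applied per course, late events after the second course are recorded but have no place in the analysis.

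Reports of adverse events are the trial's main safety measure (Study Summary). There is no safety board (9.8.2), and the PI is also the study monitor (11.1). The choice among these readings should therefore not be left until the data are in.

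**Working it through.** **Inputs.** Course length is 2 weeks, with two courses per participant (3.1). Follow-up is 12 weeks after course 1 (3.1.4), and the crossover comes after that visit (6.4.6). Follow-up after course 2 is 24 weeks (3.1.4, 6.4.6). Enrolment is up to 62, half in each order (4.5, 3.1.5).

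**Step 1: check the plan's own figures.**
- Stimulation weeks: 2 × 2 = 4. This reproduces 3.2.3 and contradicts the 2 in 8.4.4.
- End of tDCS to completion: 24 weeks by the schedule. This contradicts the 12 in 8.4.4.
- Window as written: 2 + 12 = 14 weeks, plus baseline testing.

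**Step 2: lay out the schedule.** Assume no gap between the first 12-week visit and the second course. Then course 1 is weeks 0–2, its follow-up runs to week 14, course 2 is weeks 14–16, and its follow-up runs to week 40. The minimum is 2 + 12 + 2 + 24 = 40 weeks from first stimulation. Any gap lengthens this.

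**Step 3: try each reading of 8.4.4.**

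| Reading | Stimulation weeks covered | Weeks covered | Left out |
|---|---|---|---|
| A. First course + 12 weeks | 2 of 4 | 14 of 40 (35%) | Course 2 and all its follow-up |
| B. Last course + 12 weeks | 2 of 4 | 14 of 40 (35%) | Course 1 and its follow-up; weeks 12–24 after course 2 |
| C. 2 + 12 weeks for each course | 4 of 4 | 28 of 40 (70%) | Weeks 12–24 after course 2 |

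A variant of B counts the 12 weeks back from the last visit. It also covers 2 + 12 = 14 weeks and still leaves out course 1. Every reading omits at least 40 − 28 = 12 weeks of scheduled follow-up.

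**Step 4: exposure lost under a single-course reading (A or B).** Reading A drops the real course of the sham-first half, and B drops that of the real-first half. Either way 62 / 2 = 31 of 62 real courses are lost, which is 31 × 10 = 310 of 620 planned real sessions. Reading C loses none.

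**Step 5: what that does to precision.** With no event among n real courses, the exact one-sided 95% upper bound on the risk is 1 − 0.05^(1/n).
- n = 62: 1 − 0.05^(1/62) = 4.7%
- n = 31: 1 − 0.05^(1/31) = 9.2%

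The chance of seeing at least one event at true risk p is 1 − (1 − p)^n. The documents give no rate for a rare event, so 2% below is an assumption. The 10% is the headache rate given in 12.1.
- p = 2%: 1 − 0.98^62 = 71%, against 1 − 0.98^31 = 47%
- p = 10%: 1 − 0.90^62 = 99.9%, against 1 − 0.90^31 = 96%

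Halving the exposure matters for rare events and hardly at all for detecting the common ones.

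**The case against.** The best defence is that 8.4.4 is meant per course. Sections 3.1.3 and 6.3 describe the treatment phase in the singular although there are two courses, and 6.4.6 says the second half mirrors the first. Section 8.4.4 speaks of all events and an overall analysis, and 8.5 takes the crossover population as the analysis set. This reading is natural, and under it no stimulation exposure is lost. So much of the defence stands. It does not rescue the window, because weeks 12–24 after course 2 remain outside. Section 8.5 defines people and not time, and the broad opening words of 8.4.4 are followed by a list of specific intervals.

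Three stronger inferences are tempting, and the documents do not support them.

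- *The second course is the one excluded, so the sham-first half's real stimulation goes unanalysed.* Section 8.4.4 does not identify a course. It ties its 12 weeks to the end of the study, which comes after course 2. If that points to any one course, it is the last, which would leave out the first.
- *Section 3.2.3 restricts the primary safety endpoint to the stimulation weeks.* Its four weeks belong to the sentence on collection. The endpoint sentence also covers imaging and language testing, which take place at baseline and follow-up visits outside those weeks.
- *Safety data would be lost.* Section 9.2 records events throughout the study, and 7.7 documents symptoms at every stimulation session.

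A reader might also reduce both denominators by the 25% attrition in 8.3. That assumes equal loss in both periods, which the documents do not state. Withdrawal accumulates over time, and anyone stimulated contributes safety data. No attrition-adjusted bound is given here for that reason.

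**Conclusion.** The concern holds as a contradiction in a stated analysis rule. Both figures in 8.4.4 disagree with the crossover schedule: 2 against 4 weeks of tDCS, and 12 against 24 weeks to completion. No reading tried makes them fit.

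The size depends on the reading. The window covers 14 of at least 40 weeks if it means one course, and 28 of 40 if it applies to each. The loss of 31 of 62 real courses, and the rise in the zero-event bound from 4.7% to 9.2%, apply only to a single-course reading with full enrolment and an even split of orders. Under the per-course reading the loss is 12 weeks of late follow-up and no stimulation exposure. The 40 weeks assume no gap before the crossover.

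This should be corrected before analysis. It does not affect what is collected.

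**What to change.** Replace the window in 8.4.4 with wording such as:

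> The safety analysis includes all adverse events from consent to the last study visit (Visit 35). This covers baseline testing, both 2-week stimulation courses, the 12-week follow-up after course 1 and the 24-week follow-up after course 2. Events are reported by the condition (real or sham) received in each period. Events before the first stimulation session are listed separately.

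Reporting by condition is needed because a longer pooled window alone would not show whether events followed real or sham stimulation.

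In 3.2.3, state that the four weeks describe the session-by-session questioning, and reconcile the endpoint's window with 9.2. If the primary safety endpoint is meant to be narrower than the overall analysis, say so and give its limits.

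The cost is protocol wording and a slightly larger tabulation. No visit, question or data field is added, because 9.2 already calls for these events to be recorded.

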8.5 Subject Population(s) for Analysis

The population that will be subject to analysis will be the full randomized with crossover population. Subjects that are non-compliant with treatment/crossover will be encouraged to continue with follow-up and these measurements will be enter into analysis.

9 Safety and Adverse Events

9.1 Definitions

9.1.1 Adverse Event

An **adverse event** (AE) is any symptom, sign, illness or experience that develops or worsens in severity during the course of the study. Intercurrent illnesses or injuries should be regarded as adverse events. Abnormal results of diagnostic procedures are considered to be adverse events if the abnormality:

- results in study withdrawal
- is associated with a serious adverse event
- is associated with clinical signs or symptoms
- leads to additional treatment or to further diagnostic tests
- is considered by the investigator to be of clinical significance

9.1.2 Serious Adverse Event

Adverse events are classified as serious or non-serious. A **serious adverse event** is any AE that is:

- fatal
- life-threatening
- requires or prolongs hospital stay
- results in persistent or significant disability or incapacity
- a congenital anomaly or birth defect
- an important medical event

CONFIDENTIAL

This material is the property of the University of Pennsylvania.

9.2 Recording of Adverse Events

At each contact with the participant, the researchers will seek information on adverse events by specific questioning and, as appropriate, by examination. Information on all adverse events will be recorded immediately in the source document, and also in the appropriate adverse event module of the case report form (CRF). All clearly related signs, symptoms, and abnormal diagnostic procedures results will be recorded in the source document.

All adverse events occurring during the study period will be recorded. The clinical course of each event will be followed until resolution, stabilization, or until it has been determined that the study treatment or participation is not the cause. Serious adverse events that are still ongoing at the end of the study period will be followed up to determine the final outcome. Any serious adverse event that occurs after the study period and is considered to be possibly related to the study treatment or study participation will be recorded and reported immediately to the chair of the DSMB.

